4.2.2 Secondary outcome variables

- Mortality rate from all causes at 3 and 12 months
- Mortality rate from respiratory disease at 3 and 12 months
- Mortality rate from cardiovascular disease at 3 and 12 months
- Hospitalization rate from all causes at 3 and 12 months
- Hospitalization rate with a primary diagnosis of respiratory disease or respiratory infection at 3 and 12 months
- Hospitalization rate with a primary diagnosis of cardiovascular disease at 3 and 12 months
- Rate of an incident diagnosis of cardiovascular disease at 3 and 12 months

Self-reported questionnaire data collected at 3 and 12 months:

- Self-rated oxygen utilization
- Breathlessness (Multidimensional Dyspnea Profile; MDP)
- Fatigue (FACIT-Fatigue)
- Informant-rated cognition (IQCODE and FAQ)
- Self-rated cognition (BAS)
- Health-related quality of life (CAT and EQ5D-5L)
- Global impression of change from baseline (GIC)
- Self-reported physical activity
- Preference of continuing treatment

5 Study design

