5.4.3 Questionnaire and reminder at 3 and 12 months

At 3 months (range 2 to 5 months) and 12 months (range 10 to 14 months) after randomization, all non-deceased participants (according to the Population Register) are sent a letter marked by the patients randomization number by the UCR Registry Unit (separated from the Clinical Research Unit responsible for managing of the study) which includes: 1) a standardized reminder about the allocated treatment to the patient and caregiver(s) (see study protocol, Appendix 2); 2) a questionnaire including data on smoking and on secondary endpoints (see study protocol, Appendix 3) and instructions about how to fill out and return it within 2 weeks in a stamped return envelope. If the questionnaire has not been returned to the UCR data management unit within 3 weeks, a reminder letter is sent home to the patient. The questionnaire data are entered into a database as reported (missing and incomplete data accepted) and quality checked by the UCR data management unit.

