7.6 Analysis of secondary variables

Hospitalizations are analyzed using Fine Gray regression [ref 1,2,3] accounting for death as competing event. All-cause mortality will be analyzed as the secondary outcome. Number of competing events will be presented for each analysis. Other secondary endpoints are analyzed using two-sided Student's t-tests for continuous variables (including HRQOL, breathlessness, cognition, fatigue, activity, and health care usage) and chi-2 test for categorical variables (causes of death, cognition, treatment preference). Correlational analyses, including of factors predictive of the primary and secondary outcomes will be conducted using linear regression (continuous outcomes), logistic regression (categorical outcomes), and Cox and Fine-Gray regression models (time to event outcomes).

All analyses are subject to underlying conditions – if not fulfilled due to e.g. a too small sample, it will not be attempted. Analyses of secondary variables other than the ones underlined in section 4.2.2 will be performed at Region Blekinge.

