7.7 Handling of missing data and data outside range

No imputation of missing data for variables used in the primary or secondary analyses will be performed. Only observed data will be used in the analyses.

If the date on a 3-month or 12-month form is either missing or unreadable we assume that the form was filled out at exactly 3 months or 12 months, respectively. For the PP analysis of the primary endpoint, the 3-month observation of self-reported oxygen utilization will be used if the 12-month observation is missing.

Data from forms submitted after hospitalization will not be used in the analysis of the primary outcome.

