8.1 Data sources and terminology

Swedevox include individual participant data including the date and main reason of starting LTOT; arterial blood gases (PaO₂ and PaCO₂) on air and on oxygen; in some cases the oxygen saturation (SaO₂); equipment, prescribed oxygen flow rate (liters/min); prescribed treatment duration (h/day); age; gender; height and weight (for calculation of the body mass index); performance status; and spirometry that should be representative of the patient's stable status before starting LTOT: the forced expired volume in one second (FEV1) and forced vital capacity (FVC). These data will be used for characterizing the participants at study start and for categorization into analysis groups according to severity of hypoxemia and underlying cause of starting LTOT (COPD vs. ILD).

More detailed information regarding data sources will be described in DMP (Data Management Plan)

9 Determination of sample size

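### Section 7.6 compares questionnaire scores by unadjusted observed-case t-tests, which discards the 3-month score and baseline data, loses precision, and gives no protection if non-reply depends on health differently by arm

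*SAP*

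**What the plan says.** SAP section 7.6: "Other secondary endpoints are analyzed using two-sided Student's t-tests for continuous variables"; the named outcomes are given in "t-tests for continuous variables (including HRQOL, breathlessness, cognition, fatigue, activity, and health care usage". Cognition also appears there under the chi-square test, so the point concerns outcomes analysed as scores.

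Section 7.7: "No imputation of missing data for variables used in the primary or secondary analyses will be performed", and "Only observed data will be used in the analyses". Its one stated exception is the 3-month oxygen-use value for the per-protocol analysis of the primary endpoint.

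Section 5.4.3: at each time "all non-deceased participants (according to the Population Register) are sent a letter", with one reminder. Non-reply is expected: "The questionnaire data are entered into a database as reported (missing and incomplete data accepted".

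Section 4.2.2 heads the list "Self-reported questionnaire data collected at 3 and 12 months", and the table in section 5.7 shows no questionnaire at baseline. Baseline Swedevox data are held (age, sex, blood gases, performance status, spirometry, reason for starting oxygen), but section 8.1 gives them another purpose: "These data will be used for characterizing the participants at study start and for categorization into analysis groups".

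Adjustment for age and sex (section 7.5) is confined to the primary analysis. The regressions at the end of section 7.6 concern predictive factors, not the arm comparison. The opening section says that methods for outcomes the sponsor will analyse later are set out in this SAP before database lock, so the choice is made here.

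Self-reported oxygen hours are also compared by t-test (output Table 11.7). The derived-variables appendix and the footnotes to Tables 9.1 and 11.7 let the 3-month value stand in for a missing 12-month value.

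**The concern.** The comparison at each time uses only the forms returned at that time. A patient who replied at 3 months but not at 12 contributes nothing to the 12-month comparison, although the earlier score predicts the later one. The baseline predictors are also unused.

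Two things are at stake. The first is precision. The secondary objectives in section 4.1.2 ask whether 24 h/day fails to improve or reduce each outcome, and the questionnaire t-tests carry no margin. An imprecise, non-significant result could be read as support for that framing. The second is bias. Patients know their allocation (section 5.5), so willingness or ability to reply could depend on health in a different way in each arm. The planned test could not correct for that.

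**Working it through.** **1. The plan's own figure.** The SAP states no sample size, SD, reply rate or correlation for the questionnaire outcomes. Its only calculation, in section 9.2, reproduces: (z0.95 + z0.80)² / (0.25 × ln(1.5)²) = 150.425 events, and 150.425 / 0.8 = 188.03, rounded up to 189. That concerns the composite endpoint and does not bear on this point. Apart from the planned 230 patients (115 per arm), every input below is an assumption.

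**2. Replies at 12 months.** Assume mortality of 20% to 35% and reply by 60% to 80% of survivors.
- High: 230 × 0.80 × 0.80 = 147
- Low: 230 × 0.65 × 0.60 = 90

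**3. Precision from the second time point alone.** Let rho be the 3- to 12-month correlation and p the share of 3-month responders who also reply at 12 months. Variance of the joint estimate relative to the observed-case mean is 1 − rho²(1 − p).
- rho 0.5, p 0.7: 1 − 0.25 × 0.3 = 0.925 (7.5% less)
- rho 0.5, p 0.6: 1 − 0.25 × 0.4 = 0.900 (10% less)
- rho 0.7, p 0.7: 1 − 0.49 × 0.3 = 0.853 (14.7% less)
- rho 0.7, p 0.6: 1 − 0.49 × 0.4 = 0.804 (19.6% less)

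**4. Baseline covariates alone.** Residual variance is multiplied by 1 − R². For a 0.4 SD difference with 60 per arm, power is 59% unadjusted, and 64%, 69% and 75% for R² of 0.1, 0.2 and 0.3.

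**5. Both together, by simulation.** Inputs: 115 per arm, no true difference, 25% dead, 80% reply at 3 months, about 65% of survivors replying at 12 months (115 × 0.75 × 0.65 = 56 per arm), rho 0.5 to 0.7, one baseline covariate correlated 0.4 to 0.5 with the score, 1,500 replicates. The t-test variance was 1.20 to 1.66 times that of a likelihood repeated-measures model. Two cautions apply.
- Deaths were treated as missing, so only 0.75 × 0.65 = 49% of 3-month responders had a 12-month score. Part of this gain comes from patients for whom no such score exists.
- A cruder estimator, with a separate regression in each arm and only 12-month replies that had a 3-month form, gave no gain at rho 0.5 (standard error 0.196 SD against 0.193 for the t-test) and little at 0.7 (0.182 against 0.189). The gain needs the joint likelihood model.

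**6. Bias.** In the step 5 simulation, the log-odds of reply at 12 months depended on the 3-month score, with a slope set for each arm. The t-test's bias, with a true difference of 0, was:
- equal slopes (0 and 0, or 0.5 and 0.5): within 0.01 SD
- 0 against 0.5: 0.067 to 0.103 SD
- 0 against 1.0: 0.130 to 0.191 SD
- −0.5 against 0.5: 0.137 to 0.210 SD

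A separate simulation with about 55% observed and slopes of 0.8 against 0.3 and 1.0 against 0 gave 0.094 to 0.265 SD. The combined range is about 0.07 to 0.27 SD. The repeated-measures model stayed within 0.01 SD, but by construction: reply was made to depend only on data the model uses.

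**The case against.** An observed-case t-test in a randomized comparison is legitimate, if less efficient. A reader might infer that it is valid only when reply is unrelated to health, and so is biased as planned. The documents do not support that. Step 6 shows no bias when reply depends on health equally in both arms and there is no true effect, and the SAP gives no reply rates from which a difference between arms could be shown. Nor does the 80% event rate in section 9.2 help: it is for death or hospitalization combined, and a hospitalized survivor still receives the form and the reminder.

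A reader might also infer that a repeated-measures model removes the bias entirely. It removes only the part explained by the 3-month score and baseline data. Missing at random is not simply a weaker assumption than equal selection in both arms; neither contains the other. The model also leaves truncation by death unresolved, since its 12-month mean implicitly covers patients who died.

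A long covariate list would be a poor remedy. Table 6.1 has 14 primary diagnoses and five WHO levels; with age, sex and PaO2 that is 13 + 4 + 3 = 20 parameters for perhaps 90 to 147 replies. PaO2 and performance status can be missing, and section 5.2 allows entry on saturation alone. A short collapsed set with a rule for missing covariates answers this.

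The SAP already tabulates numbers with data (section 7.4) and deaths by arm (Table 9.1), so part of the reporting exists. All these points stand as limits. None removes the precision loss, which does not depend on differential non-reply.

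**Conclusion.** The point holds as an inefficiency with a conditional risk of bias. The t-tests leave out the 3-month score and baseline predictors. Joint use of both time points cuts variance by about 7.5% to 20% under the assumptions in step 3, and baseline covariates add to that. If reply depends on health differently by arm, which is possible in a trial open to patients but not shown by the SAP, the 12-month t-test is biased by about 0.07 to 0.27 SD under the assumed slopes.

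Oxygen hours are a separate case. The 12-month comparison there is not strictly observed-case, because the appendix and table footnotes fill from 3 months while section 7.7 rules out imputation for secondary analyses. Those places contradict each other.

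These are secondary outcomes, mostly for later analysis by the sponsor. The primary conclusion is unaffected.

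**What to change.** In section 7.6, analyse each continuous questionnaire outcome with one mixed model for repeated measures: 3- and 12-month scores, arm by time, unstructured covariance. Adjust for a short pre-named set: age, sex, WHO performance status (as a score or collapsed), PaO2 on air, and COPD versus other primary diagnosis. Keep patients with a missing covariate by a missing indicator or simple baseline imputation, and amend section 7.7 to allow this. Report the arm difference at each time with a 95% CI.

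State that the model assumes missing at random, that scores after death are undefined, and that the 12-month estimate is to be read beside the numbers dead and not replying in each arm. Add a sensitivity analysis ranking death worst. Keep the t-test as a check.

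For oxygen hours, reconcile the derived-variables appendix and the footnotes to Tables 9.1 and 11.7 with section 7.7, and use only values reported at 12 months in the 12-month comparison.

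The cost is SAP wording, a standard model and an explicit missing-at-random assumption. No new data are needed.

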*Socialstyrelsen will provide us with the date of event. Time to event (in days) will be calculated by UCR

*Time to composite event (All-cause mortality/ All-cause Hospitalization)	Included in the order from Socialstyrelsen
*Time to all-cause mortality	Included in the order from Socialstyrelsen
*Time to 1st hospitalization	Included in the order from Socialstyrelsen
Mortality from respiratory disease	respiratory disease or infection (A40; J00-J99)
Mortality from cardiovascular disease	Underlying cause of death (UCD) heart disease (I00-I99)
Hospitalization from respiratory disease	UCD respiratory disease or infection (A40; J00-J99)
Hospitalization from cardiovascular disease	UCD heart disease (I00-I99)
Time to Mortality from respiratory disease	Death (from respiratory disease) date – Study start date
Time to Mortality from cardiovascular disease	Death (from cardiovascular disease) date – Study start date
Time to Hospitalization from respiratory disease	Date of hospitalization from respiratory disease – Study start date
Time to Hospitalization from cardiovascular disease	Date of hospitalization from cardiovascular disease – Study start date
Time from start until the patient stops being treated	End of treatment – Date for start of treatment
Discontinued LTOT	From Swedevox Registry
Withdrawals	DATE_OF_LTOT_WITHDRAWAL REASON_W
ITT	All randomized patients that start LTOT
PP	A randomized patient will be excluded from the PP set if LTOT has been discontinued before the primary outcome assessment or the mean LTOT utilization during follow-up to the primary endpoint is below 20 h/day for the 24 h/day group, and below 13 h/day or above 17 h/day in the LTOT 15 h/day group
COPD	J44; exacerbation: J44.0 and J44.1
Heart disease	I00-I99
Respiratory disease or infection	A40; J00-J99
fev1/fvc	FEV1/FVC
BMI	WEIGHT(kg)/(HEIGHT (m)*HEIGHT (m))
Age	Round down (RANDOMIZATION_DATE - DATE_OF_BIRTH)/365.25
Duration of treatment	Number of days with treatment during the study
Self-rated hours of oxygen	Self-reported oxygen use (mean hours/24h) is categorized using 1) average use since starting LTOT, or (if missing) mean h/day last week; using the

	questionnaire at 12 months, or (if missing) 3 months (and the described algorithm used for each time point).
Subgroup 1 Participants with more severe resting hypoxemia at LTOT start	PaO ₂ < 7.4 kPa breathing air
Subgroup 2 Participants with more moderate hypoxemia at LTOT start	PaO ₂ 7.4–8.0 kPa breathing air

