	Event rate per 100 patient-years (95% CI)	xx.x	xx.x	xx.x
	HR (95% CI) - p-value	xx.x (x.xx-x.xx) – 0.xxxx		
All-cause Hospitalization	Number of patients	xx	xx	xx
	Number of events	xx	xx	xx
	Number of competing events	xx	xx	xx
	Person-years	xxx	xxx	xxx
	Events/Participants	xx.x	xx.x	xx.x
	Event rate per 100 patient-years (95% CI)	xx.x	xx.x	xx.x
All-cause mortality	Number of patients	xx	xx	xx
	Number of events	xx	xx	xx
	Person-years	xxx	xxx	xxx
	Events/Participants	xx.x	xx.x	xx.x
	Event rate per 100 patient-years (95% CI)	xx.x	xx.x	xx.x
	HR (95% CI) - p-value	xx.x (x.xx-x.xx) – 0.xxxx		
Mortality from respiratory disease	Number of patients	xx	xx	xx
	Number of events	xx	xx	xx
	Person-years	xxx	xxx	xxx
	Events/Participants	xx.x	xx.x	xx.x
	Event rate per 100 patient-years (95% CI)	xx.x	xx.x	xx.x
	HR (95% CI) - p-value	xx.x (x.xx-x.xx) – 0.xxxx		
Mortality from cardiovascular disease	Number of patients	xx	xx	xx
	Number of events	xx	xx	xx
	Person-years	xxx	xxx	xxx

	Statistics	LTOT 24h/day	LTOT 15h/day	Total
	Events/Participants	xx.x	xx.x	xx.x
	Event rate per 100 patient-years (95% CI)	xx.x	xx.x	xx.x
	HR (95% CI) - p-value	xx.x (x.xx-x.xx) – 0.xxxx		
Hospitalization from respiratory disease	Number of patients	xx	xx	xx
	Number of events	xx	xx	xx
	Number of competing events	xx	xx	xx
	Person-years	xxx	xxx	xxx
	Events/Participants	xx.x	xx.x	xx.x
	Event rate per 100 patient-years (95% CI)	xx.x	xx.x	xx.x
	HR (95% CI) - p-value	xx.x (x.xx-x.xx) – 0.xxxx		
Hospitalization from cardiovascular disease	Number of patients	xx	xx	xx
	Number of events	xx	xx	xx
	Number of competing events	xx	xx	xx
	Person-years	xxx	xxx	xxx
	Events/Participants	xx.x	xx.x	xx.x
	Event rate per 100 patient-years (95% CI)	xx.x	xx.x	xx.x
	HR (95% CI) - p-value	xx.x (x.xx-x.xx) – 0.xxxx		

- Table 5.14 Event rate at 3 months (PP)
- Table 5.15 Event rate at 3 months (Subgroup 1)
- Table 5.16 Event rate at 3 months (Subgroup 2)
- Table 5.17 Event rate at 3 months (Subgroup 3)
- Table 5.18 Event rate at 3 months (Subgroup 4)
- Table 5.19 Event rate at 12 months (ITT)
- Table 5.20 Event rate at 12 months (PP)
- Table 5.21 Event rate at 12 months (Subgroup 1)
- Table 5.22 Event rate at 12 months (Subgroup 2)
- Table 5.23 Event rate at 12 months (Subgroup 3)
- Table 5.24 Event rate at 12 months (Subgroup 4)

Table 6 Demographics and characteristics at baseline

Table 6.1 ITT

Variable	Statistics	LTOT 24h/day n	LTOT 15h/day n	Total n	*P-value
Age (years)	n	x	x	x	0.xxx
	Mean (SD)	x (x)	x (x)	x (x)	

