	Median (IQR)		
	Min-Max		
Subgroup 4	n		
	Mean (SD)		
	Median (IQR)		
	Min-Max		

Table 9 Description of outcomes

The table below shows the descriptive data by treatment group for each outcome.

Table 9.1 ITT

	Outcome	Statistics	LTOT 24h/day n	LTOT 15h/day n	Total n
At 3 months	All-cause mortality	n(%)			
	All-cause Hospitalization	n(%)			
	Composite (All-cause mortality/ All-cause Hospitalization)	n(%)			
	Mortality from respiratory disease	n(%)			
	Mortality from cardiovascular disease	n(%)			
	Hospitalization from respiratory disease	n(%)			
	Hospitalization from cardiovascular disease	n(%)			
	Self-reported hours of oxygen* (within 24 hours)	n Mean (SD) Median (IQR) Min-Max			
At 12 months	All-cause mortality	n(%)			
	All-cause Hospitalization	n(%)			
	Composite (All-cause mortality/ All-cause Hospitalization)	n(%)			
	Mortality from respiratory disease	n(%)			
	Mortality from cardiovascular disease	n(%)			
	Hospitalization from respiratory disease	n(%)			
	Hospitalization from cardiovascular disease	n(%)			
	Self-reported hours of oxygen* (within 24 hours)	n Mean (SD) Median (IQR) Min-Max			

* Self-reported oxygen use is defined as mean hours/day. If missing, we will use mean h/day last week, using the questionnaire at 12 months, or (if missing) 3 months.

Table 9.2 PP

Table 9.3 Subgroup 1

Table 9.4 Subgroup 2

Table 9.5 Subgroup 3

Table 9.6 Subgroup 4

Table 10 Analysis of the primary variable

Table 10.1 Primary outcome

Population	Outcome	Reference group	HR (90% CI)	p-value*	p-value**
ITT	Composite event of death or 1 st hospitalization at 1 year	LTOT 15h/day	x.xx (x.xx-x.xx)	x.xx	x.xxx
PP	Composite event of death or 1 st hospitalization at 1 year	LTOT 15h/day	x.xx (x.xx-x.xx)	x.xx	x.xxx

*The p-value for the difference between treatments H0: HR=1

** The p-value corresponds to the one-sided test, at 5% significance level, that the lower limit exceeds the hypothesized value 0.67

Table 10.2 Primary outcome adjusted for sex and age

Similar table as in 10.1 repeated adjusting for sex and age (in years) at randomization. A frailty model will be performed with “center” as a random effect to account for the clustering by hospital.

Table 11 Analyses of secondary variables

Table 11.1 Secondary outcome (ITT)

Population	Outcome	Reference group	n events/competing events	HR (90% CI)	p-value*	p-value**
At 3 months	Composite event of death or 1 st hospitalization	LTOT 15h/day	xx	x.xx (x.xx-x.xx)	x.xx	x.xxx

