	All-cause mortality	LTOT 15h/day	xx	x.xx (x.xx-x.xx)	x.xx	x.xxx
	All-cause Hospitalization***	LTOT 15h/day	xx/xx	x.xx (x.xx-x.xx)	x.xx	x.xxx
	Mortality from respiratory disease	LTOT 15h/day	xx	x.xx (x.xx-x.xx)	x.xx	x.xxx
	Mortality from cardiovascular disease	LTOT 15h/day	xx	x.xx (x.xx-x.xx)	x.xx	x.xxx
	Hospitalization from respiratory disease***	LTOT 15h/day	xx/xx	x.xx (x.xx-x.xx)	x.xx	x.xxx
	Hospitalization from cardiovascular disease***	LTOT 15h/day	xx/xx	x.xx (x.xx-x.xx)	x.xx	x.xxx
At 1 year	All-cause mortality	LTOT 15h/day	xx	x.xx (x.xx-x.xx)	x.xx	x.xxx
	All-cause Hospitalization ***	LTOT 15h/day	xx/xx	x.xx (x.xx-x.xx)	x.xx	x.xxx
	Mortality from respiratory disease	LTOT 15h/day	xx	x.xx (x.xx-x.xx)	x.xx	x.xxx

	Mortality from cardiovascular disease	LTOT 15h/day	xx/xx	x.xx (x.xx-x.xx)	x.xx	x.xxx
	Hospitalization from respiratory disease***	LTOT 15h/day	xx/xx	x.xx (x.xx-x.xx)	x.xx	x.xxx
	Hospitalization from cardiovascular disease***	LTOT 15h/day	xx	x.xx (x.xx-x.xx)	x.xx	x.xxx

*** Hospitalizations are analyzed using Fine Gray regression accounting for death as competing event

Table 11.2 Secondary outcome (PP)

Table 11.3 Secondary outcome (Subgroup 1)

Table 11.4 Secondary outcome (Subgroup 2)

Table 11.5 Secondary outcome (Subgroup 3)

Table 11.6 Secondary outcome (Subgroup 4)

Table 11.7 Analysis of Self-reported hours of oxygen

Similar table as in 10.1

	Population	Outcome	Mean difference (95% CI)	p-value**
At 3 months	ITT	Self-reported hours of oxygen* (within 24 hours)	x.xx (x.xx-x.xx)	x.xx
	PP	Self-reported hours of oxygen* (within 24 hours)	x.xx (x.xx-x.xx)	x.xx
	Subgroup 1	Self-reported hours of oxygen* (within 24 hours)	x.xx (x.xx-x.xx)	x.xx
	Subgroup 2	Self-reported hours of oxygen* (within 24 hours)	x.xx (x.xx-x.xx)	x.xx
	Subgroup 3	Self-reported hours of oxygen* (within 24 hours)	x.xx (x.xx-x.xx)	x.xx
	Subgroup 4	Self-reported hours of oxygen* (within 24 hours)	x.xx (x.xx-x.xx)	x.xx
At 1 year	ITT	Self-reported hours of oxygen* (within 24 hours)	x.xx (x.xx-x.xx)	x.xx
	PP	Self-reported hours of oxygen* (within 24 hours)	x.xx (x.xx-x.xx)	x.xx
	Subgroup 1	Self-reported hours of oxygen* (within 24 hours)	x.xx (x.xx-x.xx)	x.xx
	Subgroup 2	Self-reported hours of oxygen* (within 24 hours)	x.xx (x.xx-x.xx)	x.xx
	Subgroup 3	Self-reported hours of oxygen* (within 24 hours)	x.xx (x.xx-x.xx)	x.xx
	Subgroup 4	Self-reported hours of oxygen* (within 24 hours)	x.xx (x.xx-x.xx)	x.xx

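### Section 7.6 and the output shells prescribe different analyses for respiratory and cardiovascular mortality, leave other-cause deaths unaddressed, and plan Kaplan-Meier curves where deaths compete

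*SAP*

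**What the plan says.** - Section 4.2.2 lists the outcome as "Mortality rate from respiratory disease at 3 and 12 months", with a matching line for cardiovascular disease. The derived-variables appendix defines "Time to Mortality from respiratory disease" and its cardiovascular counterpart as dates counted from study start.
- Section 7.6 assigns Fine-Gray regression to hospitalizations, "accounting for death as competing event". It then lists cause of death among the outcomes for a "chi-2 test for categorical variables (causes of death, cognition, treatment preference". It also promises: "Number of competing events will be presented for each analysis".
- Appendix 2, Table 5.13 (repeated for other populations and for 12 months) has a line "HR (95% CI) - p-value" for respiratory and cardiovascular mortality. A row counting competing events appears only under the hospitalization outcomes.
- Appendix 2, Table 11.1 gives a hazard ratio with a 90% interval and two p-values for the same mortality outcomes. Its footnote reads "Hospitalizations are analyzed using Fine Gray regression accounting for death as competing event", and the marker for it is on hospitalization rows only.
- Appendix 2, Figure 4 plans Kaplan-Meier figures for all primary and secondary outcomes.

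**The concern.** A chi-square test uses no event times and yields no hazard ratio, so section 7.6 and the shells cannot both describe the main analysis of cause-specific mortality. A patient who dies of another cause can no longer die of the named one. The plan deals with that for hospitalization but is silent on it for respiratory and cardiovascular death.

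Two things are at stake. First, which result counts is open. Section 6 places the classification into analysis populations after the analyst is unblinded, so a choice left open in the SAP could be made with allocation known. Second, Kaplan-Meier curves for an outcome with competing deaths would show an absolute risk that is too high. This applies to cause-specific mortality and to hospitalization. For hospitalization it also sits badly beside the Fine-Gray analysis that section 7.6 prescribes.

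**Working it through.** **The plan's own figures.** The SAP gives no event rate, split by cause or power for cause-specific mortality. Its one size calculation, for the composite, reproduces: ((1.645 + 0.842)/ln 1.5)² / (0.25 × 0.8) = 188.03, rounded up to 189. Nothing here depends on it.

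**1. The provisions side by side, for respiratory and cardiovascular mortality.**

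| Place in SAP | Analysis | Interval | Other-cause deaths |
|---|---|---|---|
| 7.6 | chi-square, no denominator | none | not mentioned |
| Derived variables | time to cause-specific death | – | not mentioned |
| Table 5.13 | hazard ratio, one p-value | 95% | no competing-event row |
| Table 11.1 | hazard ratio, two p-values | 90% | not marked for Fine-Gray |
| Figure 4 | Kaplan-Meier | – | not mentioned |

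The shells do not settle the text. In Table 11.1 at 1 year, cardiovascular mortality has a cell for events and competing events (xx/xx), while cardiovascular hospitalization, which carries the Fine-Gray marker, has a cell for events only (xx). At 3 months it is the other way round. The two 1-year cells look swapped.

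Tables 11.1 to 11.6 repeat the outcomes over two causes, two time points and six populations: 2 × 2 × 6 = 24 hazard ratios.

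**2. Does the choice of hazard ratio matter?** Assume constant hazards, one-year control mortality M, and a share s of control deaths from the named cause. The total hazard is L = −ln(1 − M), split into sL and (1 − s)L. Take the case with the largest shift in the range examined: M = 45%, s = 50%, no effect on the named cause (cause-specific HR 1.00), and the other-cause hazard doubled in one arm.

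- Control: L = 0.598; cumulative incidence = 0.5 × 0.45 = 0.225.
- Other arm: hazards 0.299 and 0.598, total 0.897; cumulative incidence = (1/3) × (1 − e^−0.897) = 0.197.
- Implied subdistribution HR ≈ ln(1 − 0.197)/ln(1 − 0.225) = 0.86.

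With the other-cause hazard halved instead, the cumulative incidence is 0.241 and the ratio 1.08. Over M = 15% to 45% and s = 50% to 70%, the implied subdistribution HR ran from about 0.86 to 1.08 while the cause-specific HR stayed at 1.00. The two models answer different questions, so the plan has to say which one it asks.

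**3. Does the choice of test matter?** In 2,000 simulated trials per scenario (115 per arm, s = 60%, M = 15%, 30% or 45%, no effect on the respiratory hazard, other-cause hazard halved or doubled), rejection at two-sided 0.05 was:

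- cause-specific log-rank: about 5–6%
- subdistribution log-rank: 5–8%
- chi-square on respiratory death, yes or no, among all patients: 5–9%

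The first and third differed on significance in 0.7% to 5.9% of trials. Run on all patients, the tests mostly agree.

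**4. How far would Kaplan-Meier overstate risk?** With other-cause deaths censored, one minus Kaplan-Meier estimates 1 − e^(−sL); the true cumulative incidence is sM.

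| Assumed M | L | s | 1 − Kaplan-Meier | True |
|---|---|---|---|---|
| 30% | 0.357 | 60% | 19.3% | 18% |
| 45% | 0.598 | 60% | 30.1% | 27% |
| 30% | 0.357 | 20% | 6.9% | 6% |
| 45% | 0.598 | 20% | 11.3% | 9% |

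The excess is 0.9 to 3.1 percentage points. It is relatively largest for the less common cause: 11.3/9 = 1.26.

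**The case against.** The best reply is that the plan does point to a model. Section 7.5 sets out Cox regression with a 90% interval, a one-sided p-value against 0.67 and a two-sided p-value, and refers to Tables 10 and 11. Table 11.1 has those columns, and its footnote moves only hospitalizations to Fine-Gray. The unmarked mortality rows are therefore most naturally Cox, and a Cox model that censors other-cause deaths gives a valid cause-specific hazard ratio. This stands. It does not explain what the chi-square in 7.6 is for, and it does not account for the 95% interval in Table 5.13.

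A reader might infer that the chi-square is run only in patients who died, comparing the mix of causes rather than the rate. The SAP does not say so. It gives no denominator, and Table 9.1 tabulates these deaths as n (%) by arm in the ITT population. Section 9.2 expects no loss to follow-up for the composite because of the national registries. With equally complete registry data on deaths, a chi-square on all ITT patients fairly compares cumulative incidence. A reader might also conclude that no valid analysis is planned; that does not follow either.

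The sentence promising competing-event counts could be meant for the Fine-Gray analyses alone, which is how Table 5.13 carries it out. That reading is possible, but the wording covers each analysis. The apparently swapped cells are probably a typing slip and change no method. The Kaplan-Meier figures are displays, not tests, but they are where a reader will take absolute risks from.

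**Conclusion.** The concern holds as a conflict and a gap in specification. Section 7.6 and the shells give different analyses for respiratory and cardiovascular mortality, the treatment of other-cause deaths is unstated, and the interval level differs between tables. The Kaplan-Meier figures would overstate cumulative incidence for cause-specific mortality, by roughly 1 to 3 percentage points in the cases shown. The same mechanism applies to hospitalization, where any death competes; its size was not calculated.

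These sizes rest on assumed mortality, assumed shares by cause and constant hazards, since the SAP gives none of them. The effect on significance tests is small when all ITT patients are analysed. The primary composite, its sample size and the conclusion in section 9.1 are untouched. It should be corrected before the analysis, as a matter of fixing secondary analyses in advance.

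**What to change.** 1. In 7.6, remove cause of death from the chi-square list, or keep it only as a descriptive comparison among all ITT patients.
2. Add to 7.6: respiratory and cardiovascular mortality are analysed in all ITT patients with a cause-specific Cox model, deaths from other causes being censored at the date of death. The PP and subgroup tables then follow the same model.
3. Replace the Kaplan-Meier figures for cause-specific mortality and for hospitalization with cumulative incidence curves: other-cause death competes for the former, any death for the latter. Kaplan-Meier can stay for all-cause mortality and the composite.
4. Use one interval level in Tables 5.13 and 11.1 and the tables built on them. Section 7.5 and the figure showing the non-superiority limit already use 90%.
5. Show competing-event counts for the cause-specific mortality rows, and correct the 1-year cardiovascular mortality and hospitalization cells in Table 11.1.

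The cost is a short addition to 7.6 and edits to the shells. The dates and causes of death are already in the registry data, so nothing new has to be collected.
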